3.2 Sample Size Determination

3.2.1 Supplemental Phase III Cohorts 1 and 2

A Bonferroni adjustment is used to control the overall type I error rate at 0.025 one-sided in Supplemental Cohorts 1 and 2, so each comparison of the Booster Group with the Comparator Group will be performed at one-sided significance level of 0.00833 (0.025/3). No alpha-splitting within hypothesis testing of co-primary endpoints. Assumed attrition rate of Primary Vaccination Group is 10% and Booster Group is 3% (it is anticipated that attrition to 14 days post booster will be limited and smaller than the attrition to D36 in the Comparator Group). Other assumptions for sample size calculation are as follows:

- The PsVN Std Dev is around 0.65 for primary vaccination at D36 and around 1.0 for booster vaccination at D22 on \log_{10} scale base on immunogenicity data obtained from Monogram for the corresponding assay
 - Note: The assumption of the standard deviation of the assay is based on the final interim data of D614G on the PPAS Naïve-D01+D22 at D36 and FAS NonNaïveD01 at D22 from VAT0002 Original Phase II Cohort in participants 18-55 years of age.
- For the primary and secondary objectives in terms of GMT non-inferiority against the comparator (using the D614G titers elicited by the comparator as the benchmark), the ratio of group GMT margin is 1/1.5, the assumed true ratio of group GMT for D614 containing vaccines (comparing D614G titers in both booster vaccine and priming comparator) is 1.5 (this is informed by preliminary interim data from VAT0002 Original Phase II Cohort, indicating titers generally higher in the non-naïve individuals after a single dose, compared to the titers in naïve individuals after 2 doses); and the assumed true ratio of group GMT for the B1.351 variant-containing vaccines (comparing B.1.351 titers in variant-containing vaccines versus D614G titers in the comparator D614 vaccine) is 1 (this is assumed in the absence of data).
- For the primary and secondary objectives in terms of superiority on ratio of serum neutralization titer (post-booster compared to pre-booster), the margin of ratio is 2, and the assumed true ratio is 5 (this is a conservative assumption informed by interim data from VAT0002 Original Phase II Cohort for non-naïve individuals indicating ratio of individual serum neutralization titer for D614G post single immunizations compared to baseline in the range of 14-16). Std Dev 1.0 difference on \log_{10} scale is assumed for the post/pre antibody response.
- For the conditional secondary objective in Supplemental Cohort 2 on superiority of B.1.351 strain (Booster Group versus Comparator Group), the margin of ratio is 1.5, and the assumed true ratio is 3 (this is assumed in the absence of data).
- For the conditional secondary objective on seroresponse (Booster Group at D15 versus Comparator Group at D36), the margin of proportion difference is -10%, the assumed true seroresponse rate for the Booster Group is around 96.5% (this is assumed in the absence of data) and for the Comparator Group is 99%.

For non-inferiority testing of the difference between 2 means (ratio of group GMT on \log_{10} scale), the sample size estimation used a one-sided, two-sample t-test. For superiority by a margin tests for paired means, a one-sided t-test was used.

For the vaccine groups undergoing hypothesis testing, a total of 215 participants, 18-55 years of age, are planned to be enrolled in Supplemental Cohort 1 CoV2 preS dTM-AS03 (D614) vaccine groups.

A total of 515 participants, 18-55 years old, primed with the Pfizer/BioNTech vaccine are planned to be enrolled in each of the 2 Supplemental Cohort 2 vaccine groups, CoV2 preS dTM-AS03 (B.1.351) or CoV2 preS dTM-AS03 (D614 + B.1.351).

A total of 75 participants 18-55 years of age and 25 participants ≥ 56 years of age who have received each of the priming vaccines other than those primed with Pfizer/BioNTech, Moderna, Oxford University/AstraZeneca, and J&J/Janssen, are planned to be enrolled to receive the CoV2 preS dTM-AS03 (D614) booster in Supplemental Cohort 1, and the monovalent (B.1.351) booster and CoV2 preS dTM-AS03 (D614 + B.1.351) booster in Cohort 2.

A total of 515 participants, 18-55 years of age, who are SARS-CoV-2 naïve (no evidence of previous infection or vaccination) receiving 2 doses of the CoV2 preS dTM-AS03 (D614) parental vaccine will be enrolled as the Comparator Group for both Supplemental Cohorts 1 and 2. Additionally, for enabling extrapolation, approximately 50 participants ≥ 56 years of age are planned to be enrolled in each Supplemental Cohort 1 and Cohort 2 groups primed with the Pfizer/BioNTech vaccine (in the non-exploratory arms).

Approximately 300 participants, 18-55 years of age, primed with the CoV2 PreS dTM-AS03 vaccine and 150 participants, ≥ 56 years of age, primed with the CoV2 PreS dTM-AS03 vaccine are assumed to transition from the Original Phase II Cohort into the 2 Supplemental Cohort 2 vaccine groups, CoV2 preS dTM-AS03 (B.1.351) and CoV2 preS dTM-AS03 (D614); however, the actual number of Original Phase II Cohort participants meeting eligibility criteria for transition cannot be accurately determined, and as such the actual number of CoV2 PreS dTM-AS03 booster participants in Supplemental Cohort 2 may be smaller or larger than assumed. For detailed power estimations for Supplemental Cohorts 1 and 2 refer to [Table 3.1](#).

Table 3.1: Power estimations for Supplemental Cohorts 1 and 2 (18-55 years old)

Cohort/ Objective(s)	Arm	Parameters for Non- inferiority	Parameters for Superiority	Study Power
Cohort 1 CoV2 preS dTM-AS03 (D614) Booster Group				
Primary Objectives (Type I error: 0.00833)	Pfizer primed CoV2 preS dTM-AS03 (D614) Booster Group (N=215)	
 Assumed true ratio of group GMT: 1.5 Margin: 1/1.5 Std Dev (booster): 1.0 Std Dev (comparator): 0.65 	
 Assumed true ratio: 5 Margin: 2 Std Dev (booster): 1.0 	
 Non-inferiority: 98.7% Superiority: > 99.9% Overall: 98.7%
Conditional Secondary Objectives (Type I error: 0.00833)	CoV2 preS dTM-AS03 (D614)primed CoV2 preS dTM- AS03 (D614) Booster Group (N=270)			
 Non-inferiority: 99.7% Superiority: > 99.9% Overall: 99.6%
Conditional Secondary Objectives (Type I error: 0.00833)	mRNA primed CoV2 preS dTM- AS03 (D614) Booster Group (N=290)			
 Non-inferiority: 99.8% Superiority: > 99.9% Overall: 99.8%
Conditional Secondary Objectives (Type I error: 0.00833)	Adenovirus vector primed CoV2 preS dTM-AS03 (D614) Booster Group (N=150)			
 Non-inferiority: 94% Superiority: 99.1% Overall: 93.2%
Conditional Secondary Objective (Type I error: 0.00833)	Pfizer primed CoV2 preS dTM-AS03 (D614) Booster Group (N=215)	Non-inferiority on seroresponse 
 Assumed true Comparator Group seroresponse rate: 99% Assumed actual difference between Booster and Comparator Groups: -2.5% Margin: -10% 		95.3%
Conditional Secondary Objectives	CoV2 preS dTM-AS03 (D614)primed CoV2 preS dTM- AS03 (D614)			98.9%

(Type I error: 0.00833)	Booster Group (N=270)		
Conditional Secondary Objective (Type I error: 0.00833)	mRNA primed CoV2 preS dTM-AS03 (D614) Booster Group (N=290)		99.4%
Conditional Secondary Objective (Type I error: 0.00833)	Adenovirus vector primed CoV2 preS dTM-AS03 (D614) Booster Group (N=150)		78.2%
Cohort 2 CoV2 preS dTM-AS03 (B.1.351) Booster Group			
Primary Objectives (Type I error: 0.00833)	Pfizer primed CoV2 preS dTM-AS03 (B.1.351) Booster Group (N=515)	
 Assumed true ratio of group GMT: 1 Margin: 1/1.5 Std Dev (booster): 1.0 Std Dev (comparator): 0.65 	
 Assumed true ratio: 5 Margin: 2 Std Dev (booster): 1.0 
 Non-inferiority: 80.5% Superiority: > 99.9% Overall: 80.5%
Conditional Secondary Objectives (Type I error: 0.00833)	mRNA primed CoV2 preS dTM-AS03 (B.1.351) Booster Group (N=590)		
 Non-inferiority: 84.5% Superiority: > 99.9% Overall: 84.5%
Conditional Secondary Objective on B.1.351 variant (Type I error: 0.00833)	Pfizer primed CoV2 preS dTM-AS03 (B.1.351) booster group (N=515)	
Superiority on ratio of group GMT (GMT against B.1.351 vs comparator GMT against B.1.351)
 
 Assumed true ratio of group GMT: 3 Margin: 1.5 Std Dev (booster): 1.0 Std Dev (comparator): 0.65 	> 99.9%
Conditional Secondary Objective on seroresponse (Type I error: 0.00833)	Pfizer primed CoV2 preS dTM-AS03 (B.1.351) booster group (N=515)	
Non-inferiority on seroresponse
 
 Assume true comparator group seroresponse rate: 99% Assumed actual difference between booster and comparator group: -2.5% Margin: -10% 	> 99.9%

Conditional Secondary Objective on seroresponse (Type I error: 0.00833)	mRNA primed CoV2 preS dTM-AS03 (B.1.351) booster group (N=590)			> 99.9%
Cohort 2 CoV2 preS dTM-AS03 (D614 + B.1.351) booster group				
Primary Objectives (Type I error: 0.00833)	Pfizer primed CoV2 preS dTM-AS03 (D614 + B.1.351) Booster Group (N=515)	
B.1.351 variant:
 
 Assumed true ratio of group GMT: 1 Margin: 1/1.5 Std Dev (booster): 1.0 Std Dev (comparator): 0.65 
D614 variant:
 
 Assumed true ratio of group GMT: 1.5 Margin: 1/1.5 Std Dev (booster): 1.0 Std Dev (comparator): 0.65 	
 Assumed true ratio: 5 Margin: 2 Std Dev (booster): 1.0 	
 Non-inferiority (B.1.351 variant): 80.5% Non-inferiority (D614G variant): > 99.9% Superiority: > 99.9% Overall (across two strains): 80.5%
Conditional Secondary Objectives (Type I error: 0.00833)	mRNA primed CoV2 preS dTM-AS03 (D614 + B.1.351) Booster Group (N=590)			
 Non-inferiority (B.1.351 variant): 84.5% Non-inferiority (D614 variant): > 99.9% Superiority: > 99.9% Overall (across two strains): 84.5%
Conditional Secondary Objective on B.1.351 variant (Type I error: 0.00833)	Pfizer primed CoV2 preS dTM-AS03 (D614 + B.1.351) Booster Group (N=515)	
Superiority on ratio of group GMT (GMT against B.1.351 vs comparator GMT against B.1.351)
 
 Assumed true ratio of group GMT: 3 Margin: 1.5 Std Dev (booster): 1.0 Std Dev (comparator): 0.65 		> 99.9%
Conditional Secondary Objective on seroresponse (Type I error: 0.00833)	Pfizer primed CoV2 preS dTM-AS03 (D614 + B.1.351) Booster Group (N=515)	
Non-inferiority on seroresponse
 
 Assumed true Comparator Group seroresponse rate: 99% Assumed actual difference between Booster and Comparator groups: -2.5% Margin: -10% 		> 99.9%

Conditional Secondary Objective on seroresponse (Type I error: 0.00833)	mRNA primed CoV2 preS dTM- AS03 (D614 + B.1.351) Booster Group (N=590)		> 99.9%
--	--	--	---------

Note: Std Dev of 0.65 for the comparator at D36, 1.0 for the boosters at D22 were on \log_{10} scale and 1.0 for the post/pre booster at D15 relative to D01 was on \log_{10} scale.

A total of 75 participants 18-55 years of age and 25 participants ≥ 56 years of age who have been primed with the Pfizer/BioNTech vaccine are planned to be enrolled to receive the different monovalent (B.1.351) booster formulations in Supplemental Cohort 2. The sample sizes are not based on hypothesis to be tested but rather to provide information on potential future adjustments of the booster vaccines.

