
 5) To demonstrate, in adults 18-55 years of age previously vaccinated with an adenovirus-vectored COVID-19 vaccine, that a booster dose of CoV2 preS dTM-AS03 (D614) vaccine induces an immune response that is non-inferior to the response induced by a two-dose priming series with CoV2 preS dTM-AS03 (D614) vaccine in naïve, previously unvaccinated, individuals. 6) To demonstrate, in adults 18-55 years of age previously vaccinated with adenovirus-vectored COVID-19 vaccines, that a booster dose of CoV2 preS dTM-AS03 (D614) induces an immune response that is superior to that observed immediately before booster. 	
 • Individual serum neutralizing titer against the D614G strain at D01 and D15 (group primed with adenovirus-vectored COVID-19 vaccine) • Individual serum neutralizing titer against the D614G strain at D36 (Comparator Group)
	Endpoints for secondary objectives #7 - #10:
	
 • Seroresponse rate, defined as a 4-fold-or greater rise in serum neutralization titer [post/pre] against the D614G strain, at D15 relative to D01, in each study Intervention Group • Seroresponse rate, defined as a 4-fold-or greater rise in serum neutralization titer [post/pre] against the D614G strain, at D36 relative to D01 (Comparator Group)
	Endpoints for secondary objectives #11 - #14:
	
 • Individual serum neutralizing titer at D01 and D15 against the D614G strain in each Intervention Group • Individual serum neutralization titer fold-rise postvaccination relative to D01 at D15 against the D614G strain in each Intervention Group • ≥ 2-fold-rise and ≥ 4-fold-rise in serum neutralization titer [post/pre] (fold-rise ≥ 2 and ≥ 4) at D15 relative to D01 against the D614G strain in each study Intervention Group • Seroresponse rate, defined as a 4-fold-or greater rise in serum neutralization titer [post/pre] at D15 relative to D01, against the D614G strain in each study Intervention Group
	Endpoints for secondary objective #15:
	
 • Individual serum neutralizing titer at D01 and D15 to the B.1.351 variant in each Intervention Group

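### Section 3.2.1 and Table 3.1 power the superiority and seroresponse objectives from incompatible assumptions about the same post/pre titer ratio: a 5-fold rise with log10 SD 1.0 implies about 54% seroresponse, not 96.5%.

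*SAP*

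**What the plan says.** Table 2.1 defines the endpoint for Cohort 1 as "Seroresponse rate, defined as a 4-fold-or greater rise in serum neutralization titer [post/pre] against the D614G strain, at D15 relative to D01". Cohort 2 uses the same 4-fold definition, against B.1.351 and, for the bivalent booster, D614G.

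Section 3.2.1 makes two separate assumptions that bear on this ratio:

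- For superiority of post-booster over pre-booster titers, "the margin of ratio is 2, and the assumed true ratio is 5". The 5 is called conservative against interim ratios of 14-16 in non-naïve participants of the Original Phase II Cohort. An SD of 1.0 on the log10 "scale is assumed for the post/pre antibody response". The note under Table 3.1 ties that SD to D15 relative to D01.
- For seroresponse, "the assumed true seroresponse rate for the Booster Group is around 96.5% (this is assumed in the absence of data". Against this the SAP sets a comparator rate of 99% and a margin of -10%. Table 3.1 carries this as "Assumed actual difference between Booster and Comparator Groups: -2.5"%.

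Each comparison is "performed at one-sided significance level of 0.00833 (0.025/3"). The stated seroresponse power is 95.3% (N=215), 98.9% (N=270), 99.4% (N=290), 78.2% (N=150) and >99.9% (N=515 and N=590). Section 3.4.2 takes log10 titers to be normally distributed. Nothing in the SAP links the 96.5% to the fold-rise assumptions.

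**The concern.** A seroresponse rate is a tail probability of the post/pre ratio. Once the centre and spread of that ratio are assumed, the rate follows and cannot be chosen freely. Section 3.2.1 fixes both for the superiority rows and then enters an unrelated rate for the seroresponse rows, in the same participants at the same time points. The fold-rise input is cautious where power is ample, and the seroresponse input is favourable where power is sensitive.

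At stake is what Table 3.1 tells readers about Cohort 1 secondary objectives 7-10 and Cohort 2 secondary objectives 4-5. These are formal, alpha-controlled objectives shown as well powered, but the section's other inputs point the opposite way.

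**Working it through.** **Inputs.** One-sided alpha 0.025/3 = 0.00833, margin -10%, comparator rate 99%, booster rate 96.5%, attrition 10% (comparator) and 3% (booster), all from Section 3.2.1. Evaluable comparator: 515 × 0.90, rounded down to 463. Evaluable booster: 0.97 × N, rounded down. Interval: Newcombe-Wilson score without continuity correction (Section 3.4.4), at the 98.3% level that matches this alpha.

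**Step 1: reproduce the stated power at 96.5% versus 99%.**

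| Planned N | Evaluable | Stated | Farrington-Manning | Exact Newcombe-Wilson |
|---|---|---|---|---|
| 215 | 208 | 95.3% | 95.3% | 95.1% |
| 270 | 261 | 98.9% | 98.9% | 98.6% |
| 290 | 281 | 99.4% | 99.4% | 99.2% |
| 150 | 145 | 78.2% | 78.3% | 78.8% |
| 515 | 499 | >99.9% | >99.9% | >99.9% |
| 590 | 572 | >99.9% | >99.9% | >99.9% |

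The table is right for its declared input.

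**Step 2: confirm that the superiority rows use ratio 5 and SD 1.0.** A one-sided paired t-test with effect log10(5/2)/1.0 gives 99.06% for 145 evaluable (stated 99.1%) and 99.95% for 208 (stated >99.9%). They do.

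**Step 3: rate implied by the fold-rise inputs.** With log10(post/pre) normal, P(ratio ≥ 4) = Φ[(log10 ratio − log10 4)/SD].

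- Ratio 5, SD 1.0: Φ(0.0969) = 53.9%.
- Ratio 14, SD 1.0: Φ(0.544) = 70.7%.
- Ratio 16, SD 1.0: Φ(0.602) = 72.6%.

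**Step 4: what 96.5% would require.** The normal quantile for 0.965 is 1.812.

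- SD at ratio 5: 0.0969/1.812 = 0.053.
- SD at ratios 14 and 16: 0.544/1.812 = 0.30 and 0.602/1.812 = 0.33.
- Geometric mean ratio at SD 1.0: 10^(0.602 + 1.812) = 259.

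The SAP gives no paired SD other than 1.0. As an assumed range, at ratio 15 the implied rate is 97.2% (SD 0.3), 92.4% (0.4), 87.5% (0.5), 81.1% (0.65) and 71.7% (1.0). At ratio 5 it stays between 54% and 63% for SDs from 1.0 down to 0.3.

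**Step 5: power at the implied rates.** Non-inferiority can hold only if the true booster rate exceeds 99% − 10% = 89%. At 53.9% the calculated power is below 1e-27 for every N in the table; at 70.7-72.6% it is below 1e-11.

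**Step 6: power near the assumed rate** (exact Newcombe-Wilson).

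| True booster rate | N=150 | N=215 | N=515 |
|---|---|---|---|
| 96.5% | 79% | 95% | >99.9% |
| 95% | 46% | 71% | 99% |
| 94% | 27% | 47% | 92% |
| 93% | 14% | 26% | 70% |
| 92% | 7% | 12% | 38% |
| 90% | 1% | 2% | 4% |

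**The case against.** The strongest reply is that ratio 5 with SD 1.0 was never meant as a joint forecast. The SAP calls the 5 conservative. The paired SD is assumed rather than observed: the 1.0 drawn from Phase II data is a cross-sectional titer SD at D22, not an SD of within-person change. At the cited 14-16-fold rises an SD of about 0.3 would give 96.5%, and the document cannot exclude that. This stands as far as it goes: 54% is the low-end implication of the inputs, not an estimate of the true rate. It does not reconcile the inputs, because the only paired SD stated is 1.0, and at that SD even the interim ratios leave the rate far below 89%.

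The log-normal assumption was introduced for intervals on means, and values below the quantification limit are set to half of it, so the exact tail at 4-fold is uncertain. That softens the third digit but does not close a gap of more than 20 points.

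Two stronger readings are not supported. A reader might infer that Table 3.1 is miscalculated; Step 1 shows that it is not. A reader might also infer that power is zero in every arm and that failure is to be expected. That would need actual pre-booster titers and fold-rises in previously vaccinated participants, which the SAP does not give. For the N=270 arm primed with CoV2 preS dTM-AS03, Section 3.4.4 also allows the baseline to be the Phase II D01. If that applied, the pre-booster ratio of 5 would not describe that row, although Table 2.1 speaks only of "rise in serum neutralization titer [post/pre] against the D614G strain, at D15 relative to D01".

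**Conclusion.** The concern holds as an inconsistency of assumptions, of moderate severity. Within one section, a single variable is given a distribution implying about 54% seroresponse (71-73% at the interim ratios with SD 1.0) and, separately, a rate of 96.5% with no supporting data. The stated 78.2% to >99.9% power follows from the second and is effectively nil under the first. Even setting the derivation aside, a shortfall of 1.5 points in the rate takes N=215 from 95% to 71% and N=150 from 79% to 46%.

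This rests on log-normality of the post/pre ratio, on the stated SD of 1.0 and, for N=270, on a pre-booster baseline. The seroresponse tests come last in each sequential chain, so the type I error and the power of the primary and earlier secondary objectives are unaffected.

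**What to change.** In Section 3.2.1 and Table 3.1:

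- Restate seroresponse power from one coherent post/pre ratio and paired SD. Alternatively, state the ratio and paired SD that support 96.5%, with their source.
- Show power over a range of true rates, for example 96.5, 95, 94, 92 and 90%, together with the 54-73% implied by the present inputs.
- State that power for these last-in-sequence objectives depends on an unverified rate.
- Say which D01 is the seroresponse baseline for the N=270 arm, consistently with Table 2.1 and Section 3.4.4.

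The cost is one revised table and a few sentences. The stated power is likely to look less favourable. Sample size, tests and primary power stay as they are; a smaller paired SD, if justified, would only raise the superiority power.

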3.3 Populations for Analyses

The following subgroup definitions of SARS-CoV-2 Naïve and Non-Naïve at D01 timepoint are applied for all randomized participants in all Supplemental Cohorts:

Prior SARS-CoV-2 infection status	Description
SARS-CoV-2 Naïve at baseline (Naïve-D01)	
• Negative by the anti-S immunoassay (Roche Elecsys) on D01 serum sample 
AND
 
• Negative NAAT for SARS-CoV-2 on respiratory sample collected on D01
SARS-CoV-2 Non-Naïve at baseline (Non-Naïve-D01)	
• Positive by the anti-S immunoassay (Roche Elecsys) on D01 serum sample 
OR
 
• Positive NAAT for SARS-CoV-2 on respiratory sample collected on D01

The following subgroup definitions of SARS-CoV-2 Naïve and Non-Naïve at both D01 and D22 timepoints are applied for all randomized participants in Supplemental Cohorts comparator groups:

Prior SARS-CoV-2 infection status	Description
SARS-CoV-2 Naïve at second injection (Naïve-D01+D22)	
• Negative by the anti-S immunoassay (Roche Elecsys) on D01 serum sample 
AND
 
• Negative NAAT for SARS-CoV-2 on respiratory sample collected on D01 and D22
SARS-CoV-2 Non-Naïve at second injection (Non-Naïve-D01/D22)	
• Positive by the anti-S immunoassay (Roche Elecsys) on D01 serum sample 
OR
 
• Positive NAAT for SARS-CoV-2 on respiratory sample collected on D01 or D22

The following populations are defined for analysis:

Population	Description
Screened	All participants screened for potential study enrollment will be included regardless of being enrolled or not being enrolled. The screening includes the SARS-CoV-2 rapid serodiagnosis test results, demographic information (age, ethnic/racial population, high-risk medical conditions), inclusion/exclusion criteria and prior vaccination platform for booster vaccination groups. The participants reaching the enrollment cap identified in IRT will be excluded from the study enrollment and will have no participant ID assigned.
Randomized	All participants with a randomized group that have been allocated by IRT.
Safety Analysis Set (SafAS)	Participants randomized and who have received at least one dose of the study vaccines. All participants will have their safety data analyzed after each dose according to the vaccine they truly received, and after any dose according to the vaccine received at the first dose. Safety data recorded for participants not administered a study intervention will be excluded from the analysis (and listed separately).
Full analysis set (FAS)	All randomized participants who receive at least one study injection. Participants will be analyzed according to the intervention to which they were randomized.
Per-protocol analysis set (PPAS)	Subset of the FAS. Participants presenting with at least one of the following criteria will be excluded from the PPAS: 
 • Participant did not meet all protocol-specified inclusion criteria or met at least one of the protocol-specified exclusion criteria • Participants did not receive both injections for 2 doses primary vaccination groups or 1 dose booster injection for booster vaccination groups • Participant received a vaccine other than the one that he / she was randomized to receive • Preparation and / or administration of vaccine was not done as per-protocol • Participant did not receive protocol defined vaccine in the proper time window • Participants who did not provide all post-dose blood sample within the proper time window or no post-dose blood sample was drawn • Participant received the second injection (in the primary vaccination groups) despite meeting any of the definitive contraindication criteria • Participant receives an authorized/approved COVID-19 vaccine prior to D36 for primary vaccination groups or D15 for booster vaccination groups The definition may be complemented with additional criteria for exclusion after the review of protocol deviations reported on site.


Cellular Immunity and Mucosal analysis set (CMIAS)
	
Subset of the FAS and randomly assigned to the Cellular Immunity and mucosal subset (Original Phase II Cohort, Supplemental Cohort 2 primed with Pfizer/BioNTech vaccine in the non-exploratory groups, Supplemental Cohort 2 CoV2 preS dTM-AS03 (D614) primary series from the Original Phase II Cohort). Participants presenting with at least one of the following criteria will be excluded from the CMIAS:
 
 • Participant did not meet all protocol-specified inclusion criteria or met at least one of the protocol-specified exclusion criteria • Participants did not receive both injections in the primary vaccination groups or one injection in the booster vaccination groups • Participant received a vaccine other than the one that he / she was randomized to receive • Preparation and / or administration of vaccine was not done as per-protocol • Participant did not receive vaccine in the proper time window • Participants received the second injection (in the primary vaccination groups) despite meeting any of the definitive contraindication criteria. • Participant receives an authorized/approved COVID-19 vaccine prior to D36 for primary vaccination groups or D15 for booster vaccination groups 
The definition may be complemented with additional criteria for exclusion after the review of protocol deviations reported on site.


Variant Testing analysis set (VTAS)
	
Subset of the FAS and randomly assigned to the Variant Testing subset (Supplemental Cohort 1, Supplemental Cohorts Comparator Group, Supplemental Cohort 2 primed with Pfizer/BioNTech vaccine in the non-exploratory groups, Supplemental Cohort 2 CoV2 preS dTM-AS03 (D614) primary series from the Original Phase II Cohort). Participants presenting with at least one of the following criteria will be excluded from the VTAS:
 
 • Participant did not meet all protocol-specified inclusion criteria or met at least one of the protocol-specified exclusion criteria • Participants did not receive both injections in the primary vaccination groups or one injection in the booster vaccination groups • Participant received a vaccine other than the one that he / she was randomized to receive • Preparation and / or administration of vaccine was not done as per-protocol • Participant did not receive vaccine in the proper time window • Participants who did not provide all post-dose blood samples within the proper time window or no post-dose blood sample was drawn

	
 Participants received the second injection (in the primary vaccination groups) despite meeting any of the definitive contraindication criteria. Participant receives an authorized/approved COVID-19 vaccine prior to D36 for primary vaccination groups or D15 for booster vaccination groups 
The definition may be complemented with additional criteria for exclusion after the review of protocol deviations reported on site.

--	--

